## 8 Safety and Adverse Events

### 8.1 Definitions

#### Unanticipated Problems Involving Risk to Subjects or Others

Unanticipated problems (UAPs) include, in general, any incident, experience, or outcome that meets the following criteria:

- unexpected in terms of nature, severity, or frequency given (a) the research procedures that are described in the protocol-related documents, such as the IRB-approved research protocol and informed consent document; and (b) the characteristics of the participant population being studied;

UAPs are considered to pose risk to participants or others when they suggest that the research places participants or others at a greater risk of harm (including physical, psychological, economic, or social harm) than was previously known or recognized.

#### Adverse Event

An adverse event is any untoward or unfavorable medical occurrence in a human participant, including any abnormal sign (for example, abnormal physical exam or laboratory finding), symptom, or disease, temporally associated with the participant's participation in the research, whether or not considered related to the participant's participation in the research.

#### Serious Adverse Event

Adverse events are classified as serious or non-serious. A **serious adverse event** is any AE that is:

- fatal
- life-threatening
- requires or prolongs hospital stay
- results in persistent or significant disability or incapacity
- a congenital anomaly or birth defect
- an important medical event

Important medical events are those that may not be immediately life threatening, but are clearly of major clinical significance. They may jeopardize the subject, and may require intervention to prevent one of the other serious outcomes noted above. For example, drug overdose or abuse, a seizure that did not result in in-patient hospitalization, or intensive treatment of bronchospasm in an emergency department would typically be considered serious.

All adverse events that do not meet any of the criteria for serious should be regarded as **non-serious adverse events**.

#### Adverse Event Reporting Period

The study period during which adverse events must be reported is normally defined as the period from the initiation of any study procedures to the end of the study treatment follow-up. For this study, the study treatment follow-up is defined as 30 days following the last administration of study treatment.

#### Preexisting Condition

A preexisting condition is one that is present at the start of the study. A preexisting condition should be recorded as an adverse event if the frequency, intensity, or the character of the condition worsens during the study period.

#### General Physical Examination Findings

At screening, any clinically significant abnormality should be recorded as a preexisting condition. At the end of the study, any new clinically significant findings/abnormalities that meet the definition of an adverse event must also be recorded and documented as an adverse event.

#### Post-study Adverse Event

All unresolved adverse events should be followed by the investigator until the events are resolved, the subject is lost to follow-up, or the adverse event is otherwise explained. At the last scheduled visit, the investigator should instruct each subject to report any subsequent event(s) that the subject, or the subject's personal physician, believes might reasonably be related to participation in this study.

### **Abnormal Laboratory Values**

A clinical laboratory abnormality should be documented as an adverse event if any one of the following conditions is met:

- The laboratory abnormality is not otherwise refuted by a repeat test to confirm the abnormality
- The abnormality is a grade 3 or above based on CTC 4.0

### **Hospitalization, Prolonged Hospitalization or Surgery**

Any adverse event that results in hospitalization or prolonged hospitalization should be documented and reported as a serious adverse event unless specifically instructed otherwise in this protocol. Any condition responsible for surgery should be documented as an adverse event if the condition meets the criteria for an adverse event.

Neither the condition, hospitalization, prolonged hospitalization, nor surgery are reported as an adverse event in the following circumstances:

- Hospitalization or prolonged hospitalization for diagnostic or elective surgical procedures for a preexisting condition. Surgery should **not** be reported as an outcome of an adverse event if the purpose of the surgery was elective or diagnostic and the outcome was uneventful.
- Hospitalization or prolonged hospitalization for therapy of the target disease of the study, unless it is a worsening or increase in frequency of hospital admissions as judged by the clinical investigator.

## **8.2 Recording of Adverse Events**

At each contact with the subject, the investigator must seek information on adverse events by specific questioning and, as appropriate, by examination. Information on all adverse events should be recorded in the source document, and also in the appropriate adverse event module of the case report form (CRF). All clearly related signs, symptoms, and abnormal diagnostic procedures results should be recorded in the source document.

All adverse events occurring during the study period must be recorded. The clinical course of each event should be followed until resolution, stabilization, or until it has been determined that the study treatment or participation is not the cause. Serious adverse events that are still ongoing at the end of the study period must be followed up to determine the final outcome. Any serious adverse event that occurs after the study period and is considered to be possibly related to the study treatment or study participation should be recorded and reported immediately.

### **8.2.1 Safety Assessment and Follow-Up**

The relationship to study intervention or study participation must be assessed and documented for all adverse events. Evaluation of relatedness must consider etiologies such as natural history of the underlying disease, concurrent illness, concomitant therapy, study-related procedures, accidents, and other external factors.

The following guidelines are used to assess relationship of an event to study intervention:

1. Related (Possible, Probable, Definite)
  - a. The event is known to occur with the study intervention.
  - b. There is a temporal relationship between the intervention and event onset.

- c. The event abates when the intervention is discontinued.
- d. The event reappears upon a re-challenge with the intervention.

2. Not Related (Unlikely, Not Related)

- a. There is no temporal relationship between the intervention and event onset.
- b. An alternate etiology has been established.

### **8.2.2 Expectedness**

The PI is responsible for determining whether an AE is expected or unexpected. An AE will be considered unexpected if the nature, severity, or frequency of the event is not consistent with the risk information previously described for the intervention. Risk information to assess expectedness can be obtained from preclinical studies, the investigator's brochure, published medical literature, the protocol, or the informed consent document.

### **8.2.3 Intervention**

Any intervention implemented to treat the adverse event must be documented for all adverse events.

## **8.3 Safety Reporting**

### **8.3.1 Reporting to IRB**

#### **8.3.1.1 Unanticipated Problems**

All incidents or events that meet criteria for unanticipated problems (UAPs) as defined in Section 9.1 require the creation and completion of an unanticipated problem report form (OHR-20).

UAPs that pose risk to participants or others, and that are not AEs, will be submitted to the IRB on an OHR-20 form via the eazUP system within 5 working days of the investigator becoming aware of the event.

UAPs that do not pose risk to participants or others will be submitted to the IRB at the next continuing review.

#### **8.3.1.2 Adverse Events**

Grade 1 AEs will be reported to the IRB at continuing review.

Grade 2 AEs will be reported to the IRB at the time of continuing review.

#### **8.3.1.3 Serious Adverse Events**

SAEs will be reported to the IRB on OHR-10 forms via the electronic reporting system (eSAEy) according to the required time frames described below.

Grade 3-4 AEs that are unexpected and deemed to be at least possibly related to the study will be reported to the IRB within 2 working days of knowledge of the event.

Grade 3-4 AEs that are deemed unrelated to the study will be reported to the IRB within 5 working days.

Grade 5 AEs will be reported to the IRB within one working day of knowledge of the event.

All SAEs will be submitted to the IRB at continuing review, including those that were reported previously.

### **8.3.2 Reporting to SKCC DSMC**

All AEs and SAEs, safety and toxicity data, and any corrective actions will be submitted to the DSMC per the frequency described in the SKCC DSMP. The report to the SKCC DSMC will also include any unanticipated problems that in the opinion of the PI should be reported to the DSMC.

All emergent  $\geq$  Grade 2 non-hematologic adverse events (AEs) will be reported to the DSMC. The only hematologic event which will be considered an AE/SAE for this study and will be reported is marrow aplasia (defined as <10% cellularity with <10% blast)  $>$  4 weeks not attributable to disease. Grades 1 to 4 of neutropenia, anemia, or thrombocytopenia would not qualify as an AE/SAE as the purpose of the treatment is to create a period of complete aplasia in the marrow. However, all hematologic Grade 5 SAEs will be reported to the DSMC regardless of causality.

For expedited reporting requirements, see table below:

DSMC AE/SAE Reporting Requirements

	Grade 1	Grade 2		Grade 3				Grades 4 and 5
	Unexpected and Expected	Unexpected	Expected	Unexpected		Expected		Unexpected and Expected
				With Hospitalization	Without Hospitalization	With Hospitalization	Without Hospitalization	
Unrelated Unlikely	Reviewed at Quarterly DSMC Meeting and IRB Annual Review	Reviewed at Quarterly DSMC Meeting and IRB Annual Review	Reviewed at Quarterly DSMC Meeting and IRB Annual Review	5 Working Days	Reviewed at Quarterly DSMC Meeting and IRB Annual Review	5 Working Days	Reviewed at Quarterly DSMC Meeting and IRB Annual Review	Phase I - 48 Hours (Death: 24 Hours) Phase II - 5 working days
Possible Probably Definite	Reviewed at Quarterly DSMC Meeting and IRB Annual Review	Reviewed at Quarterly DSMC Meeting and IRB Annual Review	Reviewed at Quarterly DSMC Meeting and IRB Annual Review	48 Hours (Death: 24 Hours)	Phase I - 48 Hours	48 Hours (Death: 24 Hours)	Reviewed at Quarterly DSMC Meeting and IRB Annual Review	Phase I and Phase II - 48 Hours (Death: 24 Hours)

### **8.3.3 Protocol Deviations/Exceptions**

An accidental or unintentional deviation from the approved protocol, that in the opinion of the investigator placed one or more participants at increased risk, or affects the rights or welfare of subjects, will be reported to the IRB and DSMC within 10 working days of notification of investigator. Deviations to protect subjects from immediate harm/danger should be reported immediately following the event to both the IRB and DSMC.

There may be times, when a planned deviation from the protocol seems warranted. Such deviations should only occur with the **prior** assessment of the DSMC and final approval of the IRB. All entities should be given sufficient time to evaluate the request.

### **8.3.4 Study Oversight**

In addition to the PI's responsibility for oversight, study oversight will be under the direction of the SKCC's Data and Safety Monitoring Committee (DSMC). The SKCC DSMC operates in compliance with a Data and Safety Monitoring Plan (DSMP) that is approved by the NCI.

## **8.4 Stopping Rules**

See section 7.2.

# **9 Data Handling and Record Keeping**

### **9.1 Confidentiality**

Information about study subjects will be kept confidential and managed according to the requirements of the Health Insurance Portability and Accountability Act of 1996 (HIPAA). Those regulations require a signed subject authorization informing the subject of the following:

- What protected health information (PHI) will be collected from subjects in this study
- Who will have access to that information and why
- Who will use or disclose that information
- The rights of a research subject to revoke their authorization for use of their PHI.

In the event that a subject revokes authorization to collect or use PHI, the investigator, by regulation, retains the ability to use all information collected prior to the revocation of subject authorization. For subjects that have revoked authorization to collect or use PHI, attempts should be made to obtain permission to collect at least vital status (i.e. that the subject is alive) at the end of their scheduled study period.

### **9.2 Source Documents**

Source data is all information, original records of clinical findings, observations, or other activities in a clinical trial necessary for the reconstruction and evaluation of the trial. Source data are contained in source documents. Examples of these original documents, and data records include: hospital records, clinical and office charts, laboratory notes, memoranda, subjects' diaries or evaluation checklists, pharmacy dispensing records, recorded data from automated instruments, copies or transcriptions certified after verification as being accurate and complete, microfiches, photographic negatives, microfilm or magnetic media, x-rays, subject files, and records kept at the pharmacy, at the laboratories, and at medico-technical departments involved in the clinical trial.

### **9.3 Case Report Forms**

The study case report form (CRF) is the primary data collection instrument for the study. All data requested on the CRF must be recorded. All missing data must be explained. If a space on the CRF is left blank because the procedure was not done or the question was not asked, write "N/D". If the item is not applicable to the individual case, write "N/A". All entries should be printed legibly in black ink. If any entry error has been made, to correct such an error, draw a single straight line through the incorrect entry and enter the correct data above it. All such changes must be initialed and dated. DO NOT ERASE OR

WHITE OUT ERRORS. For clarification of illegible or uncertain entries, print the clarification above the item, then initial and date it.

#### **9.4 Records Retention**

Upon completion and termination of protocol, records will be kept for a period of 5 years

### **10 Clinical Site Monitoring and Auditing**

Clinical site monitoring and auditing is conducted to ensure that the rights of human participants are protected, that the study is implemented in accordance with the protocol and/or other operating procedures, and that the quality and integrity of study data and data collection methods are maintained. Monitoring and auditing for this study will be performed in accordance with the SKCC's Data and Safety Monitoring Plan (DSMP) developed by the SKCC Data and Safety Monitoring Committee (DSMC). The DSMP specifies the frequency of monitoring, monitoring procedures, the level of clinical site monitoring activities (e.g., the percentage of participant data to be reviewed), and the distribution of monitoring reports. Some monitoring activities may be performed remotely, while others will take place at the study site(s). Appropriate staff will conduct monitoring activities and provide reports of the findings and associated action items in accordance with the details described in the SKCC DSMP.

### **11 Ethical Considerations**

This study is to be conducted according to US and international standards of Good Clinical Practice (FDA Title 21 part 312 and International Conference on Harmonization guidelines), applicable government regulations and Institutional research policies and procedures.

This protocol and any amendments will be submitted to a properly constituted independent Ethics Committee (EC) or Institutional Review Board (IRB), in agreement with local legal prescriptions, for formal approval of the study conduct. The decision of the EC/IRB concerning the conduct of the study will be made in writing to the investigator and a copy of this decision will be provided to the sponsor before commencement of this study. The investigator should provide a list of EC/IRB members and their affiliate to the sponsor.

All subjects for this study will be provided a consent form describing this study and providing sufficient information for subjects to make an informed decision about their participation in this study. See Attachment for a copy of the Subject Informed Consent Form. This consent form will be submitted with the protocol for review and approval by the EC/IRB for the study. The formal consent of a subject, using the EC/IRB-approved consent form, must be obtained before that subject undergoes any study procedure. The consent form must be signed by the subject or legally acceptable surrogate, and the investigator-designated research professional obtaining the consent.

### **12 Study Finances**

#### **12.1 Funding Source:**

The Department of Medical Oncology will be paying for this study.

#### **12.2 Conflict of Interest**

Any investigator who has a conflict of interest with this study (patent ownership, royalties, or financial gain greater than the minimum allowable by their institution, etc.) must have the conflict reviewed by a properly constituted Conflict of Interest Committee with a Committee-sanctioned conflict management plan that has been reviewed and approved by the study sponsor prior to participation in this study.

### **13 Publication Plan**

Neither the complete nor any part of the results of the study carried out under this protocol, nor any of the information provided by the sponsor for the purposes of performing the study, will be published or passed

on to any third party without the consent of the study sponsor. Any investigator involved with this study is obligated to provide the sponsor with complete test results and all data derived from the study.

We intend to publish our results in peer-reviewed journals. The primary responsibility for publication lies with the PI, co-investigator, and statistician

## 15 Attachments

Attachment 1: ECOG Performance Status

Attachment 2: Study Schedule

Attachment 3: Admissions Plan

Attachment 1:

**ECOG PERFORMANCE STATUS**

Grade	ECOG
0	Fully active, able to carry on all pre disease performance without restriction
1	Restricted in physically strenuous activity but ambulatory and able to carry out work of a light or sedentary nature, e.g., light house work, office work
2	Ambulatory and capable of all self-care but unable to carry out any work activities. Up and about more than 50% of waking hours
3	Capable of only limited self-care, confined to bed or chair more than 50% of waking hours
4	Completely disabled. Cannot carry on any self-care. Totally confined to bed or chair
5	Dead

As published in Am. J. Clin. Oncol.:

Attachment #2: Study Procedures \*

	Baseline 	Day 1 of Cycle 1	Day 4 of Cycle 1	Daily 	All cycles	Follow Up 
Informed Consent	X 					
Medical History	X 					
Physical Exam incl. weight and body surface area	X			X	X 	
Neuro exam	X					
ECOG/Performance Status	X			X		
Vital Signs	X		X	X	X 	
Height	X					
Adverse Event Assessment	X			X	X 	
LAB STUDIES						
CBC, Diff, Plts	X 	X 		X	X 	
Serum chemistry, electrolytes 	X 	X 		X	X 	
Liver function tests 	X 	X 		X 	X 	
Herpes Simplex Titer	X 					
Pregnancy Test 	X 					
Pharmacokinetics 			X 			
Pharmacodynamics	X 		X 			
TESTS & STUDIES						
Bone Marrow Biopsy	X 					X 
INVESTIGATIONAL AGENT						
Dispense Study Drug					X 	
Pill Diary Given to Patient		X			X	
Quality of Life Assessment		X 			X 	

**\*Note:**

Patients will be offered an option to complete the standard of care chemotherapy treatment at the following Jefferson Health network hospitals: Center City Hospital, Abington Hospital, Aria Hospital, Methodist Hospital and NJ Division (Kennedy) Hospital. All research related procedures are to be done at Jefferson Center City campus.

1. To be done within ten days prior to study entry unless otherwise indicated.
2. If in Hospital
3. Twice a week while out of Hospital
4. For females of child bearing potential
5. Blood to be drawn prior to Sirolimus administration for trough level on Day 4.
6. Serum chemistry and electrolytes labs should include: creatinine, BUN, glucose, magnesium, CO2, phosphate, and urate. Liver function labs should include: bilirubin, SGOT (AST), SGPT (ALT), alk phos.
7. One exam during Day 1- 10 of each cycle
8. If a diagnostic bone marrow biopsy has been done within 28 days of study enrollment, or the subject has a peripheral blast count of  $\geq 5000/\mu\text{l}$ , and a sample is available in the stem cell core registry, a repeat bone marrow biopsy and aspirate is not necessary.
9. Every 6 months from enrollment (plus or minus 10 days), until there is evidence of progression of disease or if the treating physician wants to remove the patients from the study treatment and proceed to transplant. Can be performed more frequently at investigator's discretion.
10. Labs must be done within 1 week of Day 1 of each cycle.
11. Can be done within 4 weeks of study entry.

12. Patients will be followed every 3 months for 5 years for disease status and future therapy until relapse/progression. Patients who progress/relapse will continue to be followed for survival.
13. 20 mL of peripheral blood to be collected prior to first dose of Sirolimus. Samples will also be collected within 4 hours prior to Sirolimus dose on Day 4. This will be a bone marrow aspirate if there are insufficient circulating blasts (see section 6 for details)
14. Herpes simplex titer is recommended within 4 weeks of starting.
15. Quality of life assessment will take place prior to treatment on day 1, on day 84 (cycle 3) and 164 (cycle 6) ± 30 days
16. Twice weekly
17. On treatment (days 1-10): For cycles 1-6, twice weekly labs while on treatment. After cycle 6 (if stable disease), once weekly labs performed while on treatment. Labs can be performed more frequently at investigator's discretion, if needed.
18. Off treatment (days 11-28): During cycles 1-6 once weekly labs while off treatment. After 6 cycles, if disease is stable, interim labs will be performed at the investigator's discretion if needed.
19. Day 1 of azacitidine of each cycle
20. Within 1 week of Day 1
21. Patients who elect to have standard pf care Aza/Vidaza given at Abington Hospital, Aria Hospital, Methodist Hospital or NJ Division (Kennedy) Hospital will be seen CxD1 at Center City location for study procedures and for distribution of study drug Sirolimus.

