We, along with the University of Pennsylvania have completed a phase I trial and 2 follow up trials of sirolimus with mitoxantrone, etoposide, and cytarabine in relapsed, refractory, or secondary AML. The maximum tolerated dose (MTD) was found to be a 12mg loading dose and 4mg daily dose. 27 patients were treated at this dose. Grade 3 or higher toxicities seen in patients treated at or below the MTD were neutropenic fevers in all patients, documented infections in 15 subjects, transient liver function abnormalities in three subjects, non-infectious diarrhea in two subjects, mucositis in two subjects, and transient metabolic abnormalities (hyperglycemia, hypocalcemia, hyperkalemia, hypernatremia), transient cerebellar ataxia, or thrombosis all in one subject each. We recently reported data from a phase I/II trial of the combination of sirolimus and MEC in relapsed/refractory AML that correlated response to combination therapy with baseline mTOR activation. Patients whose leukemic blasts at baseline had constitutive S6 phosphorylation and who experienced a greater than 50% reduction in the number of blast with pS6 had an impressive 67% response rate, while only 33% of those non-phosphorylated at baseline or rapamycin non-responders had a clinical response.

Our group completed a pilot trial in ALL patients combining sirolimus at the same doses with hyperCVAD and no safety issues were encountered. We have completed enrollment on a phase II trial of sirolimus MEC at Jefferson and the University of Pennsylvania and again, no safety concerns were seen therefore we believe combining this dose of sirolimus with azacitidine will not lead to unexpected toxicities.

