### 3.2.2 Secondary Endpoints

#### 3.2.2.1 Safety and tolerability

- The combination of these drugs will be deemed safe if the number of adverse events is no more than 10% greater than the additive number of events of azacitidine and sirolimus if administrated separately. This will be based upon data in the original phase 2 trials of azacitidine demonstrating an 8% toxic death rate and therefore be 18% of the total number enrolled (approx.  $40 \times 18\% = 7$ ).
- Toxicity will be graded according to the NIH CTC version 4.0 (<http://ctep.cancer.gov/reporting/ctc.html>). Toxicity refers to toxic events during the full course of treatment (through day 21) that are attributed as possibly, probably or definitely due to treatment.

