### **5 Study Drug**

#### **5.1 Sirolimus**

Drug Name: Sirolimus

Other Names: Rapamycin, Rapamune®

Classification: Immunosuppressant Agent

Mode of Action: Rapamycin inhibits T-lymphocyte activation and proliferation in response to antigenic and cytokine stimulation. Its mechanism differs from other immunosuppressants.

Storage and Stability: Store at room temperature, 20°C to 25°C (68°F to 77°F); protect from light.

Dose Specifics: Assigned dose level. Patients will receive a 12mg loading dose of sirolimus. They will then receive a 4mg daily dose of sirolimus beginning 24 hours after the loading dose for the number of days indicated by protocol regimen.

Preparation 1 and 2 mg tablet

Route of Administration: All drug is to be taken by mouth. Doses should be given every 24 hours  $\pm$  2 hours. The drug should be consistently without food. Rapamycin will be given every 24 hours for number of days indicated by protocol regimen.

Incompatibilities: Diltiazem increases serum concentrations of sirolimus. Sirolimus serum concentrations may be increased with use of voriconazole, itraconazole, ketoconazole and fluconazole. Concurrent use of these drugs is contraindicated.

Availability: Available as Rapamune® 1mg tablet and 2mg tablets. Will be available through the Investigational Drug Services.

Side Effects

**Common** (21-100% Frequency) Immediate: Nausea, Vomiting Prompt: Within 2-3 weeks, prior to next course. Diarrhea, Hypertension, Increased creatinine Delayed: Any time after above.

Hypercholesterolemia, Hypertriglyceridemia

**Occasional** (5-20% Frequency) Immediate: Rash Prompt: Within 2-3 weeks, prior to next course.

Infections; edema; weight gain, arthralgia; tremor; acne; myelosuppression; fever; abdominal pain; myalgia; hypokalemia; hypophosphatemia Delayed: Any time after above. Stomatitis

**Rare** (< 5% Frequency) Hepatotoxicity Delayed: Any time after above. Hirsutism, Secondary Lymphoma, Inflammation of the lungs

Nursing/Patient Implications: Monitor blood pressure, and serum creatinine.

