## **6 Study Procedures**

At enrollment each subject will have a medical history taken, a physical exam (including neurological exam), vital signs, ECOG performance status, and laboratory studies including CBC with differential, liver function tests, electrolytes, uric acid, and glucose as well as a pregnancy test if applicable. An HSV titer is recommended. Patients who have not had a bone marrow biopsy sample within the last 4 weeks will require a bone marrow biopsy and aspirate.

Patients will be offered an option to complete the standard of care chemotherapy treatment at the following Jefferson Health network hospitals: Center City Hospital, Abington Hospital, Aria Hospital, Methodist Hospital and NJ Division (Kennedy) Hospital. All research related procedures are to be done at Jefferson Center City campus.

Patients will be followed for disease status and survival for 5 years following the enrollment of the last patient. These follow-ups will be via phone call, chart review, or in conjunction with their routine office visits every 3 months.

See Attachment #2 for Study Procedures Table.

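### The scheduled chemistry list names no lipids, sodium, potassium or calcium, so lipid adverse events the protocol expects to be common cannot be systematically ascertained

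*Combined protocol and SAP*

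**What the plan says.** **What is measured.** The schedule in Attachment 2 has a row titled "Serum chemistry, electrolytes", at baseline, Day 1 of Cycle 1, daily in hospital and in all cycles. Its footnote, note 6, gives the content: "Serum chemistry and electrolytes labs should include: creatinine, BUN, glucose, magnesium", then CO2, phosphate and urate. Liver tests are listed separately. Note 17 adds "Labs can be performed more frequently at investigator's discretion, if needed", which concerns frequency, not content. Section 6 asks at enrollment for "laboratory studies including CBC with differential, liver function tests, electrolytes, uric acid, and glucose", plus a pregnancy test if applicable. Section 4.3 mentions screening blood chemistries without naming any.

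**What is expected.** Section 5.1 places "Hypercholesterolemia, Hypertriglyceridemia" in its common band (21-100%), as delayed effects of sirolimus, and hypokalemia in its occasional band (5-20%). Section 5.2 lists hypokalemia for azacitidine without a frequency. Among Grade 3 or higher events at or below the sirolimus maximum tolerated dose in the earlier trials, Section 1.4 reports "transient metabolic abnormalities (hyperglycemia, hypocalcemia, hyperkalemia, hypernatremia", in one subject each.

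**What must be recorded.** Under Section 8.1 a laboratory abnormality is an adverse event if, among other conditions, "The abnormality is a grade 3 or above based on CTC 4.0". Section 8.3.2 sends emergent non-hematologic adverse events of Grade 2 or higher to the monitoring committee. Neither makes an exception for lipids. Section 3.2.2.1, item g, does exclude Grade III/IV lipid abnormalities from the toxicity definition.

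**The concern.** An abnormality that shows only in a blood test is recorded only if the test is done. The protocol predicts certain laboratory abnormalities and requires them to be recorded when severe, but its schedule does not clearly require the tests that would show them.

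Safety and tolerability is a secondary objective (Section 2.2). A report with few or no lipid events would look reassuring when the reason might be that nobody looked. The same could happen with potassium, sodium and calcium at any site that ran only the named analytes.

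The list looks incomplete rather than deliberately short. Section 5.1 names hypokalemia and hypophosphatemia next to each other, and note 6 includes phosphate but not potassium.

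**Working it through.** **Step 1. Set the expected abnormalities against the tests.**

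| Analyte | Where an abnormality is expected | Named in note 6? | Covered by other wording? |
|---|---|---|---|
| Cholesterol, triglycerides | 5.1, common (21-100%) | No | No; electrolytes cannot mean lipids |
| Potassium | 5.1, occasional (5-20%); 5.2; 1.4 | No | Yes, if electrolytes is read as a class |
| Sodium | 1.4 only | No | Yes, on the same reading |
| Calcium | 1.4 only | No | Doubtful; not named as a test anywhere |
| Phosphate | 5.1, occasional | Yes | Not needed |
| Glucose | 1.4 | Yes | Not needed |

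Of the four metabolic abnormalities in Section 1.4, three (calcium, potassium, sodium) involve analytes that note 6 does not name.

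**Step 2. Ask which counts a missing test could change.**

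- *Lipids, protocol-defined toxicity.* No effect, because item g of Section 3.2.2.1 removes Grade III/IV lipid events.
- *Lipids, adverse events.* Affected, because Sections 8.1 and 8.3.2 have no such exclusion.
- *Potassium, sodium, calcium.* Grade III/IV events attributable to the investigational drug count as toxicity unless they fall under item e (due to anti-fungal drugs or tumor lysis, and correctable). A shortfall is possible, but only where a site measures the named list and nothing more.
- *Numeric safety threshold.* Section 3.2.2.1 starts from an 8% toxic-death rate and adds 10 points: 8% + 10% = 18%, and 40 × 0.18 = 7.2, which the protocol gives as 7. A laboratory value does not enter a count of toxic deaths, so this is unaffected.
- *Primary endpoint and Simon designs.* Response does not depend on these analytes. No design figure changes.

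**Step 3. Rough scale.** Expected patients = N × frequency.

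- Each lipid event, Arm A: 40 × 0.21 = 8.4 to 40 × 1.00 = 40.
- Hypokalemia from sirolimus, Arm A: 40 × 0.05 = 2 to 40 × 0.20 = 8.
- For all 74 subjects (40 + 27 + 7): 15.5 to 74 for each lipid event, 3.7 to 14.8 for hypokalemia.
- Sodium or calcium: Section 1.4 gives one subject each and no exact denominator. It says 27 were treated at the maximum tolerated dose, while the events cover patients at or below that dose. Assuming 1/27, Arm A would expect 40/27 = 1.5 for each, with chance of at least one = 1 − (1 − 1/27)^40 = 0.78. A larger denominator lowers both figures.

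The bands in Section 5.1 state no grade, dose or duration, while sirolimus here runs for 10 or 12 days of a 28-day cycle. These figures show only that the expected number is not negligible. They do not estimate Grade 3 events.

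**The case against.** The strongest reply is that note 6 is a minimum. It says what the labs should include, its row is headed "Serum chemistry, electrolytes", and Section 6 asks for electrolytes at enrollment. An electrolyte test that reported neither sodium nor potassium would be odd, and local panels may already report both, and calcium too. This largely stands for sodium and potassium: the gap is one of wording, and the documents do not show that these values go unmeasured. It is incomplete, because Section 6 speaks only of enrollment. During treatment the requirement rests on the row that note 6 defines, and a minimum list requires only what it names. It does not help lipids, and helps calcium little.

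A second reply is that the sponsor chose to treat lipid changes as non-limiting, so not measuring them is consistent. Item g does support that for toxicity. It does not reach the adverse-event rules, and excluding Grade III/IV lipid events from a count presupposes that such events may be seen.

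A third reply is that the evidence on sodium and calcium is thin: one transient event each, in trials that combined sirolimus with intensive chemotherapy. That stands. Section 1.4 also lists no Grade 3 or higher lipid event, although it does not say whether lipids were measured.

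**Conclusion.** The point holds as a minor gap in safety ascertainment. Lipid adverse events cannot be systematically ascertained, because no scheduled test measures lipids. Calcium is not required by name. Sodium and potassium are required only on a reading of electrolytes that goes beyond note 6. If local panels already report sodium, potassium and calcium, the loss is confined to lipids.

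A reader might infer more: that scheduled tests cannot detect any of these abnormalities, that toxicity is therefore undercounted, and that the safety rule leans toward declaring the combination safe. The documents do not support that. The electrolyte wording leaves room for sodium and potassium, and item g takes Grade III/IV lipid events out of protocol-defined toxicity. The opening of the safety rule does ask whether "the number of adverse events is no more than 10% greater than the additive number of events of azacitidine and sirolimus" given separately, but the protocol tabulates no such sum, so whether it contains lipid or potassium events would be a guess. The only numbers attached to the rule concern toxic deaths.

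The scale figures rest on the assumption that the frequency bands in Section 5.1 apply to this regimen, which the documents do not establish.

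**What to change.** - Reconcile note 6 with the electrolyte wording in the schedule row and Section 6, and with the listed toxicities, by naming sodium, potassium and calcium.
- Add cholesterol and triglycerides to draws already scheduled, including baseline. Section 8.1 counts a preexisting condition as an adverse event only if it worsens, so a starting value is needed to judge change. Because Section 5.1 classes the lipid effects as delayed, a baseline value alone would not show them.
- Report all these abnormalities by CTC grade. Item g can stay as it is: a lipid event can be an adverse event without being a toxicity under Section 3.2.2.1.
- For patients already treated, including the 34 (27 + 7) accrued to the closed Arms B and C, state in the report that lipids were not systematically measured, so that a low count is not read as absence of effect.

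The cost is a change to one note and a few assays on blood already being drawn. The downside is a small assay cost and a somewhat higher recorded adverse-event count. If lipids are added partway through, counts before and after the change should not be pooled without saying so.
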